5.8. Multiple Comparisons/Multiplicity

For comparisons of safety outcomes, 5%-level two-sided tests will be made. Some of these may be implicit comparisons based on the overlap of group-level confidence intervals (i.e. non-overlapping 95% CIs mean rejecting the null hypothesis of no difference between groups at the 0.05-level).

To compare primary immunogenicity outcomes (antigen-specific plasma IgG binding responses, as measured by log AUC over time) across all groups, 5%-level two-sided tests will be used. When differences are found, pairwise comparisons between vaccination groups will be made using the Bonferroni-Holm step-down procedure [1] and a 5% significance threshold for the adjusted p-values; if no difference is found across all groups, no pairwise comparisons will be made. Collapsed comparisons will be considered separately and will be made with 2.5%-level two-sided tests, even when no pairwise differences are observed.

Further exploratory comparisons for immunogenicity endpoints across all groups will be adjusted for multiplicity by a Bonferroni adjustment: multiplying p-values by the number of assays in the same set (e.g. across antigens for a given antibody test; see Section 3.2.2 for sets of assays). Then a similar process as above will be followed, with pairwise comparisons following a significant overall test and Bonferroni-Holm step-down procedure (with a 5% significance level) to account for the multiple pairwise tests.

These adjustments are intended to improve control of the type-I error across comparisons for the same outcome measure and time point (e.g. Geometric Mean Titers (GMTs) for gp120A244 plasma IgG binding at Day 14) rather than across outcome measures and/or time. This level of type-I error control will still allow for exploratory findings that would be assessed further in future studies.

6. STUDY PARTICIPANTS

6.1. Demographic and Other Baseline Characteristics

Participant demographics and baseline characteristics, listed in Section 4.9, will be summarized by vaccination group, using the statistics described in Section 5.1. Additionally, these will be summarized by clinical site.

6.2. Disposition of Participants

The number of participants who enroll in the trial, and the number and percentage of participants who complete each assessment, will be presented by vaccination group (with pooled placebo recipients). The percentage of participants who withdraw from the trial or discontinue the study drug, and reasons for withdrawal or discontinuation, will be summarized by group and given in a listing. Missed visits and withdrawals due to COVID-19 will be listed, and they will be summarized by group if there are sufficiently many of these. The impact of missing data due to COVID-19 will be discussed in the CSR.

6.3. Prior and Concurrent Medical Conditions

Prior and concurrent medical conditions, collected as part of medical history assessments, will be summarized by vaccination group. Any medical conditions reported subsequent to enrollment that meets study exclusion criteria will be presented in a listing.

6.4. Prior and Concomitant Medications

Any concomitant medications reported subsequent to enrollment that meet study exclusion criteria (see criterion #5) will be presented in a listing.

6.5. Measurements of Study Product Compliance

This is a single-dose study, so dosing non-compliance is not expected to be frequent, but any participants receiving the wrong study vaccination and those that are randomized but not vaccinated will be presented in a listing.

6.6. Protocol Deviations

All major protocol deviations will be summarized by vaccination group and presented in a listing.

7. SAFETY EVALUATION

All summaries and analysis of safety data will be presented for the Safety Population. Safety summaries will be presented by vaccination group. The denominator for the percentages may be based on the number of non-missing observations for an assessment or based on the number of participants in a population. This will be described for each exhibit.

7.1. Primary Safety Analysis

7.1.1. Unsolicited Adverse Events

Unsolicited AEs will be listed and summarized by MedDRA system order class (SOC) and preferred term (PT) for each vaccination group. These will be described overall and within 28 days post-vaccination. A participant will be counted only once per PT per reporting period. SAEs, unexpected AEs, and AESIs will be summarized and listed. The number and percentage of participants reporting each PT, along with the associated 95% exact Clopper-Pearson CI for the underlying probability of the event, will be presented.

The likelihood of reporting AEs, SAEs, and AESIs will be compared between collapsed groups (Groups 1+2 vs. Groups 3+4 to assess ALFQ safety, Groups 1+3 vs. Groups 2+4 to assess vaccine dose) via exact binomial tests. If computational challenges arise, Chi-squared tests may be used instead. Calculated confidence intervals will be used to compare pairs of individual vaccination groups, instead of formal hypothesis testing; when CIs for the same event in two groups do not overlap, this corresponds to a p-value of less than 0.05 for the analogous exact binomial test.

Unsolicited AEs will also be tabulated by investigator-determined relationship to investigational product and severity for each vaccination group.

Incident HIV infections, as diagnosed by the algorithm in Section 11.1.4.4 of the protocol, will be presented in a listing.

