5.6.1.10. Inguinal Lymph Node Biopsy

The excisional inguinal lymph node biopsy will be performed under local anesthesia by a qualified surgeon. As with all surgical procedures, there is a risk of scarring, bruising, bleeding or infection at the surgical site. These risks are minimized by the small size of the incision (approximately 1-2 centimeters), clinical evaluation to determine any additional bleeding risks (such as anticoagulant use or a congenital clotting disorder), and the adherence by the surgeon to aseptic technique. Participants may experience some discomfort following the procedure despite use of local anesthesia; for participants who complain of any subsequent discomfort, additional analgesia will be made available. There is a possibility of seroma formation at the biopsy site, which may require subsequent drainage and further management, or sensory nerve injury during the procedure, which could result in temporary or permanent local reduction in feeling. There is a small risk of chronic swelling of the leg on the side that the lymph node is taken from. For this reason, it is recommended that one participant have no more than 4 inguinal lymph node biopsies, or 2 biopsies per side, done in the subject's entire life, which would include this study, and any other studies, and any medical procedures performed elsewhere for non-research purposes. Finally, there is the unlikely possibility that the procedure will be unsuccessful and no lymph node will be recovered. This procedure will be performed by trained personnel at Chulalongkorn Hospital in Bangkok, which has a long history of safely performing lymph node biopsies on both HIV infected and healthy individuals (Chintanaphol, 2018). Only a single lymph node biopsy will be performed per participant in this study.

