⁶ The blood volumes drawn are in accordance with the Thai National Blood Bank policy: donation every 3 months but no more than 4 times a year; the amount of blood for each donation is according to weight that applies to both male and female: >50 Kg, 450 mL; ≤50 Kg, 350 mL. For participants who weigh below 50 Kg, blood for “Additional Immunogenicity Testing” will not be collected at Visits 1, 3 and 4 and only 25 mL of blood will be collected for “B-Cell Analysis” at Visits 1, 3, and 4.

⁷ Participants who consent for optional mucosal collections (semen, penile, rectal, and cervico-vaginal secretions, and cytobrush) and sigmoid biopsies will undergo additional testing for gonorrhea/chlamydia genital infections. Female participants who consent for optional mucosal collections will also undergo a pelvic examination that includes a Pap smear (if not done in 2 years prior to the mucosal collection) and visual inspection to evaluate for abnormalities. Female participants who choose to self-insert the menstrual disc collection device will be given instructions for self-insertion ([Appendix T](#)). Male participants who consent for optional mucosal collections will undergo a brief visual examination at the screening visit to assess the presence of urethral inflammation and will be given instructions for self-collection ([Appendix U](#)). Abnormalities that affect the participant’s safety or welfare or those that would increase the risk to a participant will preclude their participation in optional procedures.

⁸ Vitals to be collected both pre- and at about 30 minutes post-vaccination at Day 0.

⁹ Due to the time required to receive results of HIV testing, post-test counseling will occur at the next study visit after the results are available. HIV testing will be completed as described in Section [11.1.4.4](#) and management of positive results will be as described in Section [9.5](#).

¹⁰ Up to 10mL of blood will be drawn for safety tests within 2 days before the biopsy procedures for safety purposes. For the leukapheresis procedure, up to 10mL of blood will be drawn for safety tests within 2 days before and after the procedure for a total of 20mL of blood collected across both blood draws.

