9.1.5. Leukapheresis

Leukapheresis will be performed only at Visit 4 on participants who provide separate informed consent for the procedure. The procedure will be performed by trained personnel at the King Chulalongkorn Memorial Hospital, the Thai Red Cross AIDS Research Centre, or the Institute of HIV Research and Innovation (IHRI) Foundation.

For the leukapheresis procedure, participants will be connected to a cell separator machine via IV, which will separate white blood cells for laboratory testing while returning red blood cells either through the same needle or through a second needle placed in the opposite arm. When the procedure is completed, the maximum total red blood cell loss is about 10 mL (less than one tablespoon). Participants who undergo the leukapheresis procedure will not have blood drawn for immunogenicity assays at Visit 4. In addition to the white blood cells that are collected, approximately 150 mL of plasma will be removed at the end of each leukapheresis procedure for storage. Participants who undergo leukapheresis will have blood collected by phlebotomy in accordance with the SOE ([Table 3](#)), however they be exempted from the immunogenicity blood draw scheduled at the same visit. An additional 8.5ml of blood will be collected from these participants for PBMC and plasma storage in order to have comparator cells from each visit. Leukapheresis will be performed on participants whose platelet counts or hemoglobin counts meet the protocol inclusion criteria.

The entire procedure will take up to 2-3 hours, during which time the participant will be under constant observation by trained leukapheresis staff. If tingling in the face, lips or hands is experienced, study staff may offer calcium carbonate tablets to correct the calcium loss. Leukapheresis can occasionally cause nausea and may temporarily lower platelet count. More rarely, vomiting, fainting, seizures, dizziness, muscle cramps, itching, flushing, or burning sensation, rash, swelling of hands and feet, headache, nasal congestion, sneezing, wheezing, or chest tightness can occur. After the procedure is complete, participants will be observed for 30 minutes.

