11.3. Relationship to Investigational Product

The investigator must assign a relationship of each AE to the receipt of the investigational product. The investigator will use clinical judgment in conjunction with the assessment of a plausible biologic mechanism, a temporal relationship between the onset of the event in relation to receipt of the investigational product, and identification of possible alternate etiologies including underlying disease, concurrent illness or concomitant medications. The relationship of the vaccination to an AE will be determined based on the following definitions:

Not related: No relationship to investigational product. Applies to those events for which evidence exists that there is an alternate etiology.

Unlikely: Likely unrelated to the investigational product. Likely to be related to factors other than investigational product but cannot be ruled out with certainty.

Possible: An association between the event and the administration of investigational product cannot be ruled out. There is a reasonable temporal association, but there may also be an alternative etiology such as the participant's clinical status or underlying factors including other therapy.

Probable: There is a high degree of certainty that a relationship to the investigational product exists. There is a reasonable temporal association, and the event cannot be explained by known characteristics of the participant's clinical state or factors including other therapy.

Definite: An association exists between the receipt of investigational product and the event. An association to other factors has been ruled out.

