12. STATISTICS

12.1. Analysis Overview

This study intends to descriptively characterize safety and immune responses following delayed boosting of individuals previously vaccinated with a late boost of AIDSVAX®B/E with or without ALVAC in the RV306 protocol. Statistical analysis considers targeted enrollment into the following 5 groups:

- Placebo (n=16)
- Group 1: IHV01 and A244/AHFG Full Dose (n=16)
- Group 2: IHV01 and A244/AHFG Fractional Dose (n=16)
- Group 3: IHV01 and A244/AHFG Full Dose + ALFQ (n=16)
- Group 4: IHV01 and A244/AHFG Fractional Dose + ALFQ (n=16)

Collapsed comparisons of interest include full dose vs. fractional dose (Groups 1+3 vs. Groups 2+4) and effect of ALFQ (Groups 1+2 vs. Groups 3+4). The placebo group is included primarily for purposes of blinding safety and immunogenicity assessments, including blinded samples for the set of immunology assays. The main interest is in determining the safety of IHV01 (FLSC), A244/AHFG and ALFQ as well as whether immunologic differences can be detected between the 4 antigen-containing regimens. Response rates and, where applicable, titer level distributions with appropriate summary statistics will be estimated for each immunologic assay performed. The study will evaluate a series of cellular, humoral and mucosal immune assays. In many cases, trial specimens will be used to further evaluate the practicality of sampling, specimen processing and storage procedures combined with assay performance characteristics. As this study will enroll only participants who had completed the RV306 study, participant data from RV306 will be used in conjunction with data collected in this study to provide a more in-depth analysis of the effect of delayed boosting.

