[Additional visits]	Full IHV01/A244	x	x	x.x	x	x.x	x	x.x	x	x.x	x	x.x
	Fractional IHV01/A244	x	x	x.x	x	x.x	x	x.x	x	x.x	x	x.x
	Full IHV01/A244 + ALFQ	x	x	x.x	x	x.x	x	x.x	x	x.x	x	x.x
	Fractional IHV01/A244 + ALFQ	x	x	x.x	x	x.x	x	x.x	x	x.x	x	x.x
	Placebo	x	x	x.x	x	x.x	x	x.x	x	x.x	x	x.x
Max Severity Post Baseline	Full IHV01/A244	x	x	x.x	x	x.x	x	x.x	x	x.x	x	x.x
	Fractional IHV01/A244	x	x	x.x	x	x.x	x	x.x	x	x.x	x	x.x
	Full IHV01/A244 + ALFQ	x	x	x.x	x	x.x	x	x.x	x	x.x	x	x.x
	Fractional IHV01/A244 + ALFQ	x	x	x.x	x	x.x	x	x.x	x	x.x	x	x.x
	Placebo	x	x	x.x	x	x.x	x	x.x	x	x.x	x	x.x
Note: The “Max Post Baseline” rows indicate the maximum severity experienced by each participant at any time point post baseline, including unscheduled assessments. N = Number of participants in the Safety Population with available samples; n = Number of participants reporting each severity												

Table 28: Laboratory Summary Statistics by Visit and Vaccination Group – [Parameter]

Time Point	Vaccination Group	N	Mean	Standard Deviation	Median	Min, Max
Baseline (Day 0)	Full IHV01/A244	x	xx.x	xx.x	xx.x	xx.x, xx.x
	Fractional IHV01/A244	x	xx.x	xx.x	xx.x	xx.x, xx.x
	Full IHV01/A244 + ALFQ	x	xx.x	xx.x	xx.x	xx.x, xx.x
	Fractional IHV01/A244 + ALFQ	x	xx.x	xx.x	xx.x	xx.x, xx.x
	Placebo	x	xx.x	xx.x	xx.x	xx.x, xx.x
[Additional visits]	Full IHV01/A244	x	xx.x	xx.x	xx.x	xx.x, xx.x
	Fractional IHV01/A244	x	xx.x	xx.x	xx.x	xx.x, xx.x
	Full IHV01/A244 + ALFQ	x	xx.x	xx.x	xx.x	xx.x, xx.x
	Fractional IHV01/A244 + ALFQ	x	xx.x	xx.x	xx.x	xx.x, xx.x
	Placebo	x	xx.x	xx.x	xx.x	xx.x, xx.x
[Additional visits, Fold Change from Baseline]	Full IHV01/A244	x	xx.x	xx.x	xx.x	xx.x, xx.x
	Fractional IHV01/A244	x	xx.x	xx.x	xx.x	xx.x, xx.x
	Full IHV01/A244 + ALFQ	x	xx.x	xx.x	xx.x	xx.x, xx.x
	Fractional IHV01/A244 + ALFQ	x	xx.x	xx.x	xx.x	xx.x, xx.x
	Placebo	x	xx.x	xx.x	xx.x	xx.x, xx.x
Note: N = Number of participants in the Safety Population with results available						

IMMUNOGENICITY**Table 29: Durability of Response as Measured by Area Under the Response Curve, by Antigen and Vaccination Group – [Assay name]**

Antigen	Full IHV01/A244 (N=X)		Fractional IHV01/A244 (N=X)		Full IHV01/A244 + ALFQ (N=X)		Fractional IHV01/A244 + ALFQ (N=X)		Placebo (N=X)		p- value ^a
	n	Mean (95% CI)	n	Mean (95% CI)	n	Mean (95% CI)	n	Mean (95% CI)	n	Mean (95% CI)	
gp120 A244gD-D11	xx	xx.x (xx.x, xx.x)	xx	xx.x (xx.x, xx.x)	xx	xx.x (xx.x, xx.x)	xx	xx.x (xx.x, xx.x)	xx	xx.x (xx.x, xx.x)	0.xx

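### Unsolicited AEs caused by the optional Day 14 biopsies and leukapheresis count in the collapsed AE comparisons without procedure attribution or uptake by group, which mainly exposes the ALFQ contrast

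*SAP*

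**What the plan says.** **Comparison.** SAP 7.1.1, under the primary safety analysis, says: "The likelihood of reporting AEs, SAEs, and AESIs will be compared between collapsed groups". The contrasts are Groups 1+2 vs 3+4 for ALFQ and Groups 1+3 vs 2+4 for dose. SAP 5.8 sets the level: "For comparisons of safety outcomes, 5%-level two-sided tests will be made". Unsolicited AEs are described overall and for the first 28 days. Protocol 12.2.3 names the ALFQ contrast as a key comparison.

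**What counts as an AE.** Protocol 11.2.1 takes any adverse change after injection, related or not. Protocol 11.7.1 collects AEs to the end of the study.

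**Procedures.** Leukapheresis, sigmoid biopsy and lymph node biopsy are optional and take place only at Day 14 (Protocol Synopsis and Table 3). The protocol describes their harms. For lymph node biopsy, Protocol 5.6.1.10 says "there is a risk of scarring, bruising, bleeding or infection at the surgical site". For leukapheresis, Protocol 9.1.5 says: "Leukapheresis can occasionally cause nausea and may temporarily lower platelet count".

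**Attribution.** Protocol 11.3 says: "The investigator must assign a relationship of each AE to the receipt of the investigational product". Neither document asks for a relationship to a study procedure.

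**Laboratory.** Table 3, footnote 10, adds bloods for leukapheresis participants: "up to 10mL of blood will be drawn for safety tests within 2 days before and after the procedure". The SAP Table 27 note says that its maximum-severity rows "indicate the maximum severity experienced by each participant at any time point post baseline, including unscheduled assessments".

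**The concern.** A wound problem after lymph node excision, or nausea after leukapheresis, is an unsolicited AE like any other in the SAP 7.1.1 comparison. It can also enter the Table 15 row for unexpected AEs within 28 days, which is not restricted to product-related events. Some events will be hard to separate: the injections go into the thigh, the node biopsy is inguinal, and local reactions after Day 7 are reported as AEs (Protocol 11.2.2).

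The two contrasts differ in exposure.

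- **ALFQ.** Groups 3 and 4 open only after Groups 1 and 2 have filled (Protocol 5.9), and staff know which stage includes ALFQ (Protocol 7.3.2, SAP 4.5.5). The Synopsis gives the study of ALFQ effects in lymph nodes as the purpose of the node biopsies, so recruitment effort for them could plausibly differ by stage. Randomization does not balance uptake across this contrast, and a difference in uptake could be read as an ALFQ safety effect.
- **Dose.** Full and fractional dose enrol together and blinded, and Table 3 places optional-procedure consent at screening. Uptake is balanced in expectation. Procedure events then add the same background to both arms, which dilutes a real difference and leaves room for chance imbalance.

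**Working it through.** **Inputs from the documents.** There are 16 active participants per group (Protocol 12.1), so each collapsed contrast is 32 vs 32. Tests are two-sided at 5% (SAP 5.8). SAP 7.1.1 names exact binomial tests; I used Fisher's exact test, enumerating all outcomes.

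**Plan's own figure.** For 0 events in n, the Clopper-Pearson upper limit is 1 − 0.025^(1/n). This gives 20.6% for n=16 and 10.9% for n=32, as in Protocol Table 7. The plan's stated figures are not in dispute.

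**Assumed inputs.** The documents give no background AE risk (b), procedure uptake (u) or AE rate per procedure (q). With independent causes:

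P(AE) = 1 − (1 − b)(1 − u·q)

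**No product effect, b = 20%, uptake 20% vs 50%.**

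| q | Lower-uptake arm | Higher-uptake arm | Difference (points) | False rejection |
|---|---|---|---|---|
| no procedures | 20.0% | 20.0% | 0 | 2.4% |
| 10% | 1 − 0.8×0.98 = 21.6% | 1 − 0.8×0.95 = 24.0% | 2.4 | 3.0% |
| 20% | 1 − 0.8×0.96 = 23.2% | 1 − 0.8×0.90 = 28.0% | 4.8 | 4.3% |
| 60% | 1 − 0.8×0.88 = 29.6% | 1 − 0.8×0.70 = 44.0% | 14.4 | 16.1% |

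At a more extreme uptake split of 10% vs 60%, false rejection is 3.7%, 7.2% and 42.8% for q = 10%, 20% and 60%.

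**Equal uptake, no product effect.** At 30% in both arms, false rejection stays between 2.0% and 3.2% for b from 10% to 50% and q from 20% to 80%. There is no inflation.

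**Equal uptake, true AE risks 10% vs 40%.**

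| u, q | Observed risks | Power |
|---|---|---|
| none | 10.0% vs 40.0% | 75% |
| 30%, 20% | 1 − 0.9×0.94 = 15.4% vs 1 − 0.6×0.94 = 43.6% | 63% |
| 30%, 50% | 1 − 0.9×0.85 = 23.5% vs 1 − 0.6×0.85 = 49.0% | 48% |

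**Rare event types.** Six procedure events against none (6/32 vs 0/32) give p = 0.024; five against none give p = 0.053. In a group of 16 with no other events, two procedure events move the exact interval from 0–20.6% to 1.6–38.3%.

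**The case against.** The strongest reply is that the plan already limits the problem.

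- Investigators weigh alternative causes for every AE (Protocol 11.3 and 11.7.1). SAP Tables 25 and 26 split related from unrelated events, Table 15 has a row for related unexpected AEs, and Listing 9 shows an alternate etiology for SAEs. This stands as partial mitigation, but no planned comparison uses the alternate cause.
- Table 15 has no row for any unsolicited AE, so the contrast modelled above matches the SAP 7.1.1 text rather than a table row. Whether a biopsy event counts as unexpected depends on the Investigator's Brochure and Clinical MOP (Protocol 11.2.4), which are not in the documents. That is why the point says only that such events can enter that row.
- A 60% AE rate per procedure fits poorly with a protocol that calls leukapheresis reactions rare (5.6.1.11) and describes sigmoid biopsy bleeding as slight and usually self-limiting (5.6.1.9). This stands. At 10–20% and uptake of 20% vs 50%, false rejection remains below 5%.
- The study describes itself as exploratory and descriptive. That lowers the stakes, but product safety is still its primary objective.

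A reader might infer that the whole primary safety endpoint is contaminated, that laboratory drops bias the group tests, or that the dose comparison measures who had a procedure. The documents support none of these. Solicited reactogenicity covers the first 7 days (SAP 7.1.2). Laboratory values are summarized without a between-group test and reach the AE comparison only if clinically significant and reported as AEs (SAP 7.1.3). Dose allocation is concurrent and blinded.

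**Conclusion.** The point holds in a limited form. Procedure-caused unsolicited AEs enter the collapsed comparisons, and the planned tables would not let a reader separate them from product effects or see whether uptake differed. The ALFQ contrast can be biased if uptake changes between stages; the dose contrast faces dilution and chance imbalance only.

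The size cannot be determined from the documents. Under 20% background risk and 20% vs 50% uptake, false rejection runs from 3.0% to 16% as the procedure-AE rate goes from 10% to 60%. The upper figure needs both a high procedure-AE rate and a wide uptake gap, and should not be read as an expected value. Power loss at equal uptake (75% to 63% or 48%) rests on the assumed rates in the same way.

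This is a cheap improvement to the analysis and not a flaw that invalidates the design.

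**What to change.** 1. Keep the all-cause comparison as the main analysis.
2. For each AE, record relationship to each optional procedure. The CRF is not in the documents; if it cannot be changed, recorded etiologies and procedure dates may serve.
3. Report uptake of each procedure by group next to Table 15.
4. Add two sensitivity repeats of the collapsed AE comparisons to SAP 7.1.1 and Table 15: one omitting procedure-attributed AEs, and one cutting follow-up at the procedure date. The second needs no attribution judgement. It shortens follow-up more where uptake is higher, so show observation time by group beside it.
5. In Table 27, flag the safety draws taken within 2 days after leukapheresis and show maximum severity with and without them. Do not drop all unscheduled samples until the next visit: between Day 14 and Day 168 these could include the repeat CD4 assay, at least 4 weeks later, that Protocol 7.6.1 uses to confirm a decline.

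The cost is one CRF field, some SAP wording and a little more analysis. Attribution is a judgement by staff who know ALFQ status, which is why excluding attributed events should not become the main comparison.

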12.2.3. Safety Analysis

AEs will be listed individually and summarized by body system and preferred terms within a body system for each treatment group. Serious and/or unexpected AEs will also be discussed on a case-by-case basis. For the tabulation of the AEs by body system, a participant will be counted only once in a given body system. For example, a participant reporting nausea and diarrhea will be reported as one participant, but the symptoms will be listed as 2 separate AEs within the class. Therefore, the total number of AEs reported within a body system may exceed the number of participants within the body system reporting AEs. AEs will also be described by time period (i.e., overall and within 28 days of vaccination).

The occurrence of local and systemic reactogenicity symptoms, AEs and SAEs will be assessed as the proportions of participants experiencing such safety events along with 95% CIs. A key comparison of interest is between participants receiving vaccination with and without ALFQ (i.e., Groups 1+2 vs. Groups 3+4). Between group and collapsed comparisons will be performed using a chi-square (or exact test as appropriate).

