12.4. Level of Significance to be Used

Five percent level two-sided tests will be used when comparing safety and primary immunogenicity outcomes. Secondary and exploratory outcomes will control for multiplicity as appropriate for each analysis.

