4.2. Discussion of Study Design, Including the Choice of Control Groups

This study uses a factorial, placebo concurrent control design to assess the safety and immunogenicity of varying doses of the same vaccine with or without the ALFQ adjuvant. This is a Phase I study with a primary objective of characterizing the safety of the study vaccination, so saline placebo was chosen as the control.

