4.4.2. Allocation of Participants to Study Arms (Randomization)

A randomization schedule will be centrally generated by the protocol statistician. The study will recruit approximately equal numbers of males and females, but formal targets for randomization will not be established. **Table 1** shows the planned vaccination group allocation.

Randomization is stratified by clinical site, with a separate list generated for each site. Blocks will be used within each stratum to maintain balance in assignments over time.

Randomized participants who withdraw before receiving study vaccination will be replaced, with the replacement participant receiving the same assignment.

After the protocol amendment to reduce the total sample size, implemented in version 5.0 of the protocol, a new set of assignments was generated for Groups 3 and 4 based on the updated allocation ratios. Randomization into Groups 1 and 2 was stopped prior to the initial target, to approximately maintain these new group sizes.

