7.1.2. Solicited Reactogenicity Events

The occurrence of local and systemic reactogenicity symptoms will be assessed similarly to unsolicited AEs, with the number and proportion of participants experiencing each safety event at any point during the reactogenicity period (first 7 days after vaccination), along with the associated exact 95% CI. Collapsed comparisons will be made as in Section 7.1.1 as well.

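### The SAP's safety comparison of individual groups by 95% CI overlap is labelled a 5%-level test, but at about 16 per group it flags only Fisher p-values below roughly 0.003 to 0.005, and it replaces the test named in the protocol

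*SAP*

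**What the plan says.** SAP 7.1.1 compares the collapsed groups (ALFQ against no ALFQ, full against fractional dose) with exact binomial tests. For any two individual groups it says "Calculated confidence intervals will be used to compare pairs of individual vaccination groups, instead of formal hypothesis testing", using 95% Clopper-Pearson intervals, and adds that non-overlap corresponds to p<0.05 on the analogous exact test.

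SAP 5.8 sets two-sided 5%-level tests for safety outcomes and says some of these may be implicit, through interval overlap, because "non-overlapping 95% CIs mean rejecting the null hypothesis of no difference between groups at the 0.05-level".

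Protocol 12.2.3 says "Between group and collapsed comparisons will be performed using a chi-square (or exact test as appropriate"), and Protocol 12.4 says "Five percent level two-sided tests will be used when comparing safety and primary immunogenicity outcomes". SAP section 11, where changes in planned analyses would be recorded, is a heading without text.

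On placebo, SAP 4.2 says the primary objective is "characterizing the safety of the study vaccination, so saline placebo was chosen as the control". Protocol 12.1 says "The placebo group is included primarily for purposes of blinding safety and immunogenicity assessments". Placebo recipients form the fifth analysis group.

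**The concern.** Two separate 95% intervals can overlap although a direct comparison of the groups gives p well below 0.05. Non-overlap is therefore a far stricter criterion than a 5% test. SAP 7.1.1 calls the check a replacement for testing, while SAP 5.8 uses the language of rejection at 0.05. Neither section says what overlap means, so a reader of 5.8 may take it as a negative 5% test.

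At stake is whether intermediate safety differences between two regimens, or between a regimen and placebo, are flagged when the protocol's own test would flag them. The Table 15 shell has p-values for the two collapsed contrasts only and no placebo column, so overlap is the only rule left for comparing any regimen with placebo.

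How far the check reaches is itself unclear. SAP 5.8 covers safety outcomes in general. SAP 7.1.2 says "The occurrence of local and systemic reactogenicity symptoms will be assessed similarly to unsolicited AEs" but expressly carries over only the collapsed comparisons.

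**Working it through.** **Inputs.** 16 per active group and 16 pooled placebo (Protocol 12.1; SAP 4.1); 95% Clopper-Pearson intervals (SAP 7.1.1); two-sided 5% level (SAP 5.8; Protocol 12.4). The two-sample exact test is taken as the two-sided Fisher test. Sizes of 14 to 18 were also checked, because SAP 4.4.2 says "Randomization into Groups 1 and 2 was stopped prior to the initial target, to approximately maintain these new group sizes".

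**Formulas.** For x events in n, the lower limit is the 2.5% quantile of Beta(x, n−x+1), or 0 if x=0. The upper limit is the 97.5% quantile of Beta(x+1, n−x), or 1 if x=n. A pair is flagged if one group's upper limit lies below the other's lower limit. Size and power are sums of Bin(x₁; n₁, p₁) × Bin(x₂; n₂, p₂) over the flagged tables.

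**The plan's own figure.** For 0/16 the upper limit is 1 − 0.025^(1/16) = 20.6%, as in SAP Table 3. The other cells of that table also reproduce.

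**One boundary by hand.** The lower limit is 19.8% for 7/16 and 24.7% for 8/16. So 0/16 overlaps 7/16 (19.8% < 20.6%) although Fisher p=0.0068. It separates only from 8/16 (p=0.0024).

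**All 17 × 17 = 289 tables at 16 against 16**

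| Quantity | Result |
|---|---|
| Fisher p<0.05 | 122 |
| Intervals do not overlap | 76 |
| Fisher p<0.05 but intervals overlap | 122 − 76 = 46 (38%) |
| Intervals do not overlap, Fisher p≥0.05 | 0 |
| Largest p among flagged tables | 0.0038 (3/16 v 12/16) |
| Smallest p among unflagged tables | 0.0059 (1/16 v 9/16) |
| Maximum size, overlap / Fisher | 0.21% / 2.0% |

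At this size the flagged set is exactly the set with p<0.005. Unflagged examples: 0/16 against 5, 6 or 7 (p=0.043, 0.018, 0.0068), and 1/16 against 7, 8 or 9 (p=0.037, 0.016, 0.0059).

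**All 15 size combinations from 14 to 18 per group.** The largest flagged p is 0.0027 to 0.0053; 35% to 44% of the tables with p<0.05 are missed; maximum size is 0.15% to 0.29% (Fisher 1.8% to 4.1%).

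**Power at 16 against 16.** The documents give no per-participant event rates by arm, so all rates here are assumptions. The nearest figure is in Protocol 5.5.1: 241 − 196 = 45 of 241 injections (19%), vaccine and placebo pooled, with some reactogenicity.

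| Assumed rates | Overlap | Fisher |
|---|---|---|
| 10% v 50% | 22% | 58% |
| 19% v 50% | 8.5% | 30.5% |
| 19% v 60% | 23% | 53% |
| 19% v 70% | 46% | 76% |
| 20% v 60% | 21% | 50% |
| 20% v 90% | 91% | 99% |
| 10% v 90% | 98.8% | 99.9% |
| 10% v 15% | <2% | <2% |

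The loss is in the middle range. Very large contrasts, such as the near-universal local pain and tenderness that Protocol 5.5.3 reports with ALFQ, are flagged almost equally by either rule. For small differences neither rule has power.

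**The case against.** The SAP disclaims formal testing for these pairs, its one-way statement is true, and a rule of size 0.2% is valid at 5%. The study is descriptive. The ALFQ contrast that Protocol 12.2.3 singles out, and the dose contrast, keep exact tests with 32 per side: Fisher power there is 68% for 19% v 50%, 94% for 10% v 50% and 89% for 20% v 60%, if those rates hold across the pooled groups. Placebo is there mainly for blinding, and neither document names a regimen-against-placebo safety test. Unadjusted Fisher tests on ten pairs bring false flags, whereas Holm over ten pairs starts at 0.05/10 = 0.005 and would flag nearly what overlap flags. Protocol 12.7 lets a deviation be described in the study report, so an empty SAP section 11 is not in itself a breach. No pause or stopping decision uses the check, and every group's counts and intervals are shown.

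Much of this stands, and it limits the point to interpretation. The 38% counts tables equally and is not a probability of missing a real effect. A strict pairwise standard would also be defensible, but the SAP does not give that as its reason. None of this makes the check the 5% comparison that SAP 5.8 describes, or reconciles it with the between-group test in Protocol 12.2.3. Calling it a non-test in 7.1.1 and a rejection rule in 5.8 remains a contradiction.

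**Conclusion.** The concern holds and should be fixed. The check controls false positives, but it is far less sensitive than the 5% label suggests: its working cut-off is a Fisher p of about 0.003 to 0.005 for groups of 14 to 18. At the intermediate contrasts assumed above, its power is roughly 22 to 36 percentage points below Fisher's (8.5% v 30.5% up to 22% v 58%). It also departs from Protocol 12.2.3 without a recorded reason and leaves no formal safety comparison of any regimen with placebo.

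The table counts rest only on group size, the Clopper-Pearson intervals and the choice of Fisher as the exact test. The power figures rest on assumed rates. The collapsed contrasts and trial conduct are unaffected.

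**What to change.** In SAP 5.8 and 7.1.1, remove interval overlap as a 5%-level test. For individual pairs, including each regimen against placebo, report two-sided Fisher p-values, as Protocol 12.2.3 allows. Limit them to any local, any systemic, any solicited and any unsolicited event, any SAE and any AESI, and label them unadjusted. Say in 7.1.2 whether this applies to solicited events. Keep the Clopper-Pearson intervals as description and state that overlap is not evidence of no difference. Risk differences are optional.

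The cost is SAP wording and one table of 10 pairs × 6 endpoints = 60 p-values. If all five groups share a true rate of 20% to 50%, the chance of at least one Fisher p<0.05 among the ten pairs is about 12% to 14% per endpoint (overlap 0.4% to 1.9%). For the four placebo pairs alone it is about 6% to 7%.

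If the sponsor prefers Holm over ten pairs, or keeps the overlap check, it should say so openly, drop the 5% label, and record the departure in SAP section 11 and, under Protocol 12.7, in an amendment or the study report. Holm does not recover the lost sensitivity: in simulation at assumed rates of 10/30/30/60/60% in the five groups, the mean number of pairs flagged per endpoint was 3.02 for unadjusted Fisher, 1.31 for Holm and 1.27 for overlap.

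The minimum is three sentences: correct the 5% label, say overlap is inconclusive, and record the departure. That leaves the intermediate differences unflagged.
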